2.2. Protocol Violations

At the discretion of the Sponsor, major protocol violations, as determined by a review of the data may result in the removal of a patient's data from the PP Set. The Sponsor or designee will be responsible for producing the final protocol violation file (formatted as a Microsoft Excel file), in collaboration with Veristat and the data monitoring group as applicable; this file will include a description of the protocol violation and clearly identify whether or not this violation warrants exclusion from the PP Set. This file will be finalized prior to database

lock.

All protocol violations will be presented in a data listing.

3. GENERAL STATISTICAL METHODS

3.1. Sample Size Justification

It is estimated that at least 5 patients within each subgroup of RGDO will be recruited. Given the rarity of these disorders, the sample size is not driven by statistical considerations, but primarily driven by clinical considerations. Therefore, estimated power for expected weight change will not be provided, and efficacy will be only summarized. P-values and confidence intervals may be provided wherever is appropriate, but these should be considered for estimation and clinical scrutiny purpose, instead of formal statistical hypothesis testing purpose.

3.2. General Methods

All data listings that contain an evaluation date will contain a relative study day (Rel Day). Pre-treatment and on-treatment study days are numbered relative to the day of the first dose of study medication which is designated as Day 1. The preceding day is Day -1, the day before that is Day -2, etc.

All output will be sorted and labeled according to the International Conference on Harmonisation recommendations and formatted to the appropriate page size(s).

Tabulations will be produced for appropriate demographic, baseline, efficacy, and safety parameters. For categorical variables, summary tabulations of the number and percentage of patients within each category of the parameter will be presented. For continuous variables, the number of patients (N), mean, median, standard deviation (SD), minimum, and maximum values will be presented.

Data that was collected prior to amendment 9 that will no longer be collected under amendment 9 or thereafter, will be provided in by-patient listings. Summary tables may be provided as appropriate.

3.3. Computing Environment

Unless otherwise noted, all descriptive statistical analyses will be performed using SAS® statistical software Version 9.4 (SAS Institute Inc., Cary, NC, USA) or higher. Medical history and AEs will be coded using Medical Dictionary for Regulatory Activities (MedDRA). Concomitant medications will be coded using World Health Organization (WHO) Drug Dictionary.

3.4. Baseline Definitions

The last value (or last week of values for weekly average hunger scores) obtained prior to the first dose of study drug will be considered the baseline for all endpoints. If there is insufficient hunger score data prior to first dose of study drug, Week -1 or Day 1 will serve as baseline; hunger score data prior to Week -1 will not be considered for baseline.

3.5. Methods of Pooling Data

The data from this study may be pooled with other studies based on genetic/disease indication as appropriate. If the appropriate pooling will be needed, the analysis strategy will be addressed in the pivotal study SAP.

3.6. Adjustments for Covariates

No formal statistical analyses that adjust for possible covariate effects are planned.

3.7. Multiple Comparisons/Multiplicity

Multiplicity is not of concern for this study with a descriptive interpretation.

3.8. Subpopulations

All primary, secondary, and exploratory endpoints will be examined separately for each specific subgroup of RGDO.

In addition, data cuts looking at sub-populations within each subgroup of RGDO may be further examined. Examples may include:

- Age
 - ≥ 18 years old/ < 18 years old
 - ≥ 18 years old/ $12 - < 18$ years old/ < 12 years old
- Sex (male, female), body mass index (BMI) or other demographic factors
- Type or pathogenicity of genetic variants

3.9. Withdrawals, Dropouts, Loss to Follow-up

Patients will be informed that they have the right to withdraw from the study at any time for any reason, without prejudice to their medical care. The Investigator also has the right to withdraw patients from the study if it is medically appropriate in the opinion of the investigator.

3.10. Missing, Unused, and Spurious Data

In general, there will be no substitutions made to accommodate missing data points. All data recorded on the case report form (CRF) will be included in data listings that will accompany the CSR.

When tabulating AE data, partial dates will be handled to more accurately determine whether an event was treatment-emergent.

AE start dates that are missing or incomplete will be handled as follows:

(1) Missing Day Only

- If the month and year are the same as the month and year of the first dose date, the first dose date will be used.
- If the month and year are before the month and year of the first dose date, the last day of the month will be assigned to the missing day.
- If the month and year are after the month and year of the first dose date, the first day of the month will be assigned to the missing day.

(2) Missing Day and Month

- If the year is the same as the year of the first dose date, the first dose date will be used.

- If the year is prior to the year of the first dose date, December 31 will be assigned to the missing fields.
- If the year is after the year of first dose date, January 1 will be assigned to the missing fields.

(3) Missing Day, Month, and Year

- The first dose date will be used.

If the stop date is non-missing and the imputed start date is after the stop date, the stop date will be used as the start date. If the stop date is missing and the imputed start date is after a patient's date of discontinuation, the date of discontinuation will be used.

AE stop dates that are missing or incomplete will be handled as follows:

(1) Missing Day Only

- The last day of the month will be assigned as the missing day.

(2) Missing Day and Month

- December 31 will be assigned to missing fields.

[figure not shown]
(3) Missing Day, Month, and Year

- The event will be regarded as ongoing.

If the start date is non-missing and the imputed stop date is before the start date, the start date will be used. If the death date is available and the imputed stop date is after the death date, the death date will be used.

3.11. Visit Windows

It is expected that all visits should occur according to the protocol schedule. For patients enrolled prior to amendment 9, visits should start to transition towards the post-amendment 9 SOA as outlined in [Section 1.3.1](#). All data will be tabulated per the evaluation visit as recorded on the CRF even if the assessment is outside of the visit window. If the evaluation visit is missing in the database but there are data from an unscheduled or additional visit that is inside the visit window, the data from the unscheduled or additional visit will be used in data summaries. If a patient discontinues or completes the study prior to having their visits updated to align with the post-amendment 9 schedule of assessments, then the patient's visits will be mapped in accordance with the amendment 9 schedule of assessments as outlined in a separate document. All available data will be listed for each patient.

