1.3. Study Design

1.3.1. Synopsis of Study Design

This is a Phase 2, proof-of-concept study to assess initial safety and efficacy of setmelanotide within each identified subtype of rare genetic disorders of obesity (RGDO) and on suspected genetic mutations associated with obesity. All these conditions are: homozygous or compound heterozygous LEPR mutations, heterozygous POMC mutations, POMC hypermethylation variants, Bardet-Biedl syndrome or Alström syndrome, Smith-Magenis syndrome, SH2B1 haploinsufficiency, carboxypeptidase E deficiency, SRC1 mutations, leptin deficiency obesity,

MC4R deficiency obesity, PCSK1 deficiency obesity, chromosomal rearrangement of the 16p11.2 locus causing obesity, and potential additional RGDO cohorts provided they are collected in the database.

The study design is dependent upon time of enrollment, with a new study design being implemented for patients enrolling under amendment 9 and thereafter. Patients enrolled prior to amendment 9 will eventually transition to amendment 9 schedule of events.

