For pre-amendment 9 patients, the treatment phase of the study will begin with an initial period of dose titration in 0.5 mg increments and lasting between 2 and 12 weeks. The dosing will range from as brief as a single dose step at either 1.0 mg for adults or 0.5 mg for adolescent (ages 12 – 18 years) patients, to as many as 5 (adults) or 6 (adolescents) dose steps to reach 3.0 mg once-daily. The highest potential dose allowed in dose titration, however, is expected to be 2.5 mg, with the option to progress further to 3.0 mg if there is a lack of response at 2.5 mg. Thus, each patient will have his/her dose individualized depending on the number of dosing increments administered, where each individual patient's therapeutic dose will be established by upwards dose titration in 2-week intervals. Thereafter, patients will continue on active treatment at their optimal therapeutic dose for an additional 10 weeks, for a total combined dosing duration of 12 weeks at the individual patient's established therapeutic dose [i.e., the last 2 weeks during dose titration plus 10 weeks of open label treatment]. Patients will complete all procedures as described [Table 1-1](#), [Table 1-2](#), [Table 1-3](#). Patients who demonstrate at least 5 kg weight loss at the end of the Open Label Treatment Period (or 5% weight loss for patients with baseline body weight < 100 kg) will continue onto the long-term (1 year) extension period. It is planned that the individual patient's therapeutic dose, established during the initial period of dose titration, will continue throughout the study. In consenting patients, a 2- to 4-week period of active treatment withdrawal will be included during the 1-year extension.

Thus, pre-amendment patients will progress sequentially through the study as depicted in [Figure 1](#).

For post-amendment 9 patients, upon providing informed consent, patients will enter the Screening Period. During the Screening Period, patients will be assessed for eligibility and complete all screening procedures as described in [Table 2](#). Each patient's genetic information will be reviewed by the Sponsor to confirm the patient is eligible for the study. During the Screening Period, each patient will be instructed to complete a hunger questionnaire on a daily basis and will be required to have completed at least four days of the questionnaire prior to first dose.

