Eligible patients will return to the clinic within 2 – 8 weeks of completing the Screening Visit for the Baseline Visit (Visit 2) and first dose of setmelanotide. Dose levels for all patients will escalate to a final dose of 3.0 mg/day during an initial dose-titration phase, but the starting dose will depend on patient age. Patients 6 up to 16 years old will initially be dosed at 1.0 mg/day for 2 weeks, beginning at the Baseline Visit on Study Day 1. Starting on Day 15, the dose will escalate to 2.0 mg/day and remain at that level for 2 weeks, until the patient returns to clinic for Visit 3 on Day 29. At Visit 3, the dose will be escalated to 3.0 mg/day; the patient will continue dosing at 3.0 mg/day for 12 weeks. Patients ≥16 years old will initiate dosing at 2.0 mg/day at the Baseline Visit, and continue dosing at that level for 2 weeks. The dose will be escalated to 3.0 mg/day beginning on Study Day 15, and the patient will continue that dose for 14 weeks. Study site staff will call all patients at their homes after the first 2 weeks of treatment to ensure the escalation occurred as planned and collect any adverse events (AEs).

Patients will continue dosing at 3.0 mg/day and return to the clinic every four weeks (Visits 3-5) to complete the assessments in [Table 2](#). After 16 weeks in the study, patients will return to the clinic for Visit 6. At Visit 6, the patient will receive the last setmelanotide injection.

Participation in the study will then conclude in one of the following two ways:

- Complete Visit 6 and enroll in a separate extension study, Rhythm Study RM-493-022. If RM-493-022 is not yet open at the clinic site, the patient will continue daily setmelanotide injections and other activities per the current study, as presented in the Schedule of Assessments (SOA) ([Table 2](#)). The patient will return to the clinic for Bridging Visits every 12 weeks for up to one year, until the extension study opens at the site. Additional clinic visits may be scheduled at the discretion of the primary investigator (PI).
- Decide not to participate in the extension study and proceed to the final study visit (Visit 7) in 4 weeks.

Patients on study prior to amendment 9 should transition to dose escalation as outlined in protocol amendment 9 in the manner outlined below:

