- 6 The Dose Titration phase will be a variable schedule lasting a minimum of 2 weeks in which patients will return to the clinic approximately every 2 weeks in order to establish the individual patient's therapeutic dose according to Protocol. Given the variable number of dose titration steps in the Dose Titration Phase, each Dose Titration Visit Number (V) will remain V2 with an alphabetized suffix added to each titration visit (i.e.; first dose titration at start of Week 1 = V2a, second dose titration at start of Week 3 = V2b, etc.). This will allow for the Visits to be appropriately tracked. Additionally, each dose titration visit will have the same pre and post dose assessments as outlined in the SOA (with the exception of Anti-Rm-493 antibodies, metabolic and hormonal assays, ECG, Inclusion/Exclusion review and Medical History Review).
- 7 Once the patient's individual therapeutic dose is established the patient will enter the Open Label Active Treatment phase for 10 additional weeks, for a combined total of 12 weeks of dosing at the therapeutic dose. During this time, the study calendar will be reset, starting when the therapeutic dose was initiated (i.e. the last 2 weeks of dose titration when the therapeutic dose was established). Therefore, the Open Label Active Treatment phase starts at the beginning of Week 3 (V2x – final dose titration visit). Patients losing 5 kg of weight (or 5% if baseline weight is < 100 kg) at the end of the Open Label Treatment phase will be eligible to enter the one-year extension.
- 8 During the titration period and the 10-week Open Label Treatment Period, patients (and/or parents/guardians) will measure blood pressure and heart rate at home once daily prior to dosing in the morning, and record the values. The measurements should be taken in triplicate and all 3 readings recorded. If needed, Rhythm will supply a blood pressure machine for these readings.

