4.3.2. Secondary Analyses

Body Weight (kg):

Descriptive statistics for the actual, change and percent change from baseline in body weight (kg) will be presented for patients of the FAS for all visits by subgroup of RGDO and overall.

Daily Hunger Scores:

Descriptive statistics for the actual and change from baseline in the weekly average of the daily hunger score for non-cognitively impaired patients in the FAS will be provided for all weeks by subgroup of RGDO. Descriptive statistics for the actual and change from baseline in the weekly average of the daily hunger score for patients in the FAS will be provided for the ~3 month analysis endpoint (identified as per handling approach of primary efficacy endpoint) by RGDO for exploratory purposes.

Prior to summarization, daily hunger scores for each of the 3 hunger assessments for patients ≥ 12 years of age will be averaged separately by week. For patients < 12 years of age, there is only one daily hunger assessment to be averaged by week. For a week of hunger scores to be considered evaluable, scores need to be recorded and available for analysis on at least 1 of 7 days to provide sufficient data to determine mean values. If sufficient data is not available to determine mean values, mean hunger score for that week will be considered missing.

Descriptive statistics for the actual and change from baseline in the weekly average of the daily hunger score for patients in the FAS will also be provided for all weeks by subgroup of RGDO and where scores need to be recorded and available for analysis on at least 3 of 7 days. If sufficient data is not available to determine mean values, mean hunger score for that week will be considered missing.

Global Hunger Scores:

Global Hunger Scores will be summarized by visit by subgroup of RGDO. Shift from baseline in global hunger score for patients in the FAS will be provided by subgroup of RGDO by visit.

Waist Circumference (cm):

Descriptive statistics for the actual and change from baseline in waist circumference (cm) for patients in the FAS will be provided for all visits by subgroup of RGDO.

[REDACTED]

A series of black horizontal bars of varying lengths, likely representing data or text that has been redacted or obscured. The bars are arranged vertically and appear to be of different widths, suggesting they represent different pieces of information or different lines of text. The black bars are set against a white background.

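### By-visit tables follow CRF visit labels, and Visit 7 is an on-drug visit before Amendment 9 but an off-drug visit after it, so V7 summaries could pool unlike data

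*SAP*

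**What the plan says.** SAP 3.11 makes the CRF label the basis of tabulation: "All data will be tabulated per the evaluation visit as recorded on the CRF even if the assessment is outside of the visit window". The same section has one exception. For patients who discontinue or complete before their visits have been brought into line with the new schedule, "visits will be mapped in accordance with the amendment 9 schedule of assessments as outlined in a separate document". SAP 1.3.1 adds that "Patients enrolled prior to amendment 9 will eventually transition to amendment 9 schedule of events".

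The two schedules use the same visit numbers on different calendars.

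- **Before Amendment 9 (SAP Tables 1-2 and 1-3):** V4, V5, V6 and V7 are at Days 29, 57, 85 and 141. Footnote 7 to these tables says that "the study calendar will be reset, starting when the therapeutic dose was initiated". Titration is described in SAP 1.3.1 as "lasting between 2 and 12 weeks", and its last two weeks count towards time at the therapeutic dose. V7 belongs to the one-year extension, and Table 1-3 marks study treatment as given at that visit.
- **After Amendment 9 (SAP Table 2):** V4, V5, V6 and V7 are at Days 57, 85, 113 and 141, counted from first dose. SAP 1.3.1 places the last injection at V6. Patients who do not join the extension study "proceed to the final study visit (Visit 7) in 4 weeks".

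SAP 4.3.2 states that body-weight statistics "will be presented for patients of the FAS for all visits by subgroup of RGDO and overall". Waist circumference and global hunger are also summarized by visit and subgroup, and SAP 4.6.4 summarizes vital signs by visit. None of these tables is split by amendment.

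**The concern.** A by-visit mean can be interpreted only if the label stands for one exposure state. Here one label covers two designs. The exception in SAP 3.11 is limited to patients who leave before their visits are updated, yet the SAP expects the other earlier-enrolled patients to move across. Nothing says what happens to visits those patients had already completed under the old numbering.

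V7 matters most because drug status differs, not only timing. The patients are also selected in opposite directions: before Amendment 9 they are early responders who qualified for the extension; after it they are people who stop treatment and do not enter the extension study. A pooled V7 mean would describe neither group. Protocol 8.1 expects 1 to 15 patients per subgroup, so one or two such records could move a subgroup mean noticeably.

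**Working it through.** **Inputs.** Visit days come from SAP Tables 1-2, 1-3 and 2. The titration range is in SAP 1.3.1 and the calendar reset in footnote 7. SAP 2.1 and 4.3.1 define the first therapeutic dose: for later patients it is the date of Visit 3, and dosing at the preceding level lasts "until the patient returns to clinic for Visit 3 on Day 29" (SAP 1.3.1, for the younger age group). The plan gives no figure of its own on this point to reproduce.

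**Formulas.** Study Day d is d − 1 days after the day on which its calendar starts.

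- Pre-Amendment 9, start of therapeutic dose: (titration weeks − 2) × 7 days after first dose. For 2 weeks this is 0; for 12 weeks it is 70.
- Pre-Amendment 9, days since first dose: (d − 1) + 0 to 70. Days since first therapeutic dose: d − 1.
- Post-Amendment 9, days since first dose: d − 1. Days since first therapeutic dose: d − 29.

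| Visit | Nominal day, pre / post | Days since first dose, pre / post | Days since first therapeutic dose, pre / post |
|---|---|---|---|
| V4 | 29 / 57 | 28–98 / 56 | 28 / 28 |
| V5 | 57 / 85 | 56–126 / 84 | 56 / 56 |
| V6 | 85 / 113 | 84–154 / 112 | 84 / 84 |
| V7 | 141 / 141 | 140–210 / 140 | 140 / 112 |

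**V4 to V6.** Nominal days differ by 28 (57 − 29, 85 − 57, 113 − 85). Time since first dose differs by an amount that depends on titration length. On the SAP's therapeutic-dose clock the visits coincide. That match rests on the Visit 3 convention: patients aged 16 or over reach 3.0 mg on Day 15, so their time at that dose at V4, V5 and V6 is 57 − 15 = 42, 85 − 15 = 70 and 113 − 15 = 98 days.

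**V7.** In the post-Amendment 9 schedule, days off drug = 141 − 113 = 28. In the pre-Amendment 9 schedule, treatment is given at the visit, so days off drug = 0. (The optional 2- to 4-week withdrawal can fall either side of V7, but its visits A, B and C have their own labels.) Both schedules collect weight, waist, vital signs and global hunger at V7. Table 1-3 shows no safety laboratory tests or ECG at pre-Amendment 9 V7, so those summaries are not exposed there.

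**Matching on nominal day does not help.** V7 is Day 141 in both schedules. A map that paired visits by nominal day would put on-drug and off-drug values in the same row.

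**One patient, two V7s.** The transition rules in SAP 1.3.1 allow an earlier-enrolled patient who is past 16 weeks to proceed to the final Visit 7. Such a patient may already have had the on-drug V7.

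**Size.** If a share p of the V7 records is on drug, with mean m_on against m_off for the rest, the pooled mean differs from the off-drug mean by p × (m_on − m_off). The documents give none of the three quantities.

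**The case against.** A fair defence has five parts.

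1. *The mapping may already deal with this.* It sits in a separate document that was not available. The wording of SAP 3.11 could also imply that everyone who stays does have their visits updated. This stands to the extent that a reader might infer that part-way patients certainly keep their old labels, and the SAP does not say so. But it gives no rule for their earlier visits either, and the stated default is the CRF label.
2. *The labels agree on the clock that matters.* A reader might infer that V4 to V6 are simply different times in the two designs. The documents do not support that without qualification: by the SAP's own definition they fall at 28, 56 and 84 days in both. This stands, with the limit noted above for patients aged 16 or over. It does not rescue V7.
3. *The main analyses are not affected.* Correct. The primary endpoint and the ~3-month weight and hunger summaries are chosen by a 60- to 120-day window, and daily hunger is tabulated by week. Pre-Amendment 9 global hunger was not scheduled at V4 or V5, so it cannot mix there.
4. *Re-binning everything by days since first dose would do harm.* Also correct. After a 12-week titration, a patient in the V6 slot at 112 days would have 112 − 70 = 42 days at therapeutic dose, against 84 for a post-Amendment 9 patient. In the V4 slot at 56 days, that patient would be 70 − 56 = 14 days short of starting it.
5. *These are descriptive secondary tables in an exploratory study, with dated listings by patient.* True, and it limits the consequence. But the tables are what will be read, and a listing does not correct a row that combines treated and untreated patients.

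**Conclusion.** The concern holds for V7 and for the gap in the mapping rule. As written, SAP 3.11 allows secondary by-visit summaries of weight, waist, global hunger and vital signs at V7 to pool on-drug values from extension patients with values taken about 28 days after the last dose in patients not entering the extension study. It has no rule for the earlier visits of patients who transition part-way.

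The conclusion rests on reading the CRF-label rule as the default wherever the stated exception does not apply, and on at least some pre-Amendment 9 patients having V7 data. How much mixing would occur cannot be computed. A reader might infer that the trial's main result is compromised or that a rebound analysis is spoiled. The first does not follow, because the primary endpoint does not use visit labels. The second describes an analysis that the visible text does not plan. The change should be made, but it concerns secondary and safety tables only.

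**What to change.** Amend SAP 3.11 as follows.

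- Apply the Amendment 9 visit mapping to every pre-Amendment 9 record, including those of patients who later transitioned.
- Put the map in the SAP and state the clock it uses. Make that clock consistent with the first-therapeutic-dose definition in SAP 4.3.1, or show time since first dose and time since first therapeutic dose side by side.
- Tabulate by the derived analysis visit instead of the CRF label.
- Use dosing dates to classify each record as on or off treatment, and report post-treatment V7 values in an off-treatment row separate from all on-treatment visits.

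The cost is SAP wording and routine programming from dates already collected. No new data are needed.
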